## STATISTICAL ANALYSIS PLAN

**TITLE: Postpartum Non-pharmacologic Pain Management – Randomized Controlled Trial**

**INVESTIGATORS:** [name] (PI), [name], [name], DO, [name]

July 27, 2022

NCT03903172

Statistical analysis will consist of comparison of the study groups (Abdominal binder vs Standard of care) on:

- 1) baseline characteristics including age and baseline pain score.
- 2) study outcomes for average pain score on postpartum day 0 and postpartum day 1.
- 3) postpartum non-narcotic pharmacologic medication use.
- 4) narcotic pharmacologic pain medication used.

Analysis will be as follows:

- 1) Baseline age and postpartum pain scores will be analyzed using Student's T-test.
- 2) Average pain scores on PPD0 and PPD1 will be analyzed using Student's T-test.
- 3) Postpartum non-narcotic pharmacologic medications will be compared using Chi square.
- 4) Post partum narcotic pharmacologic medication use will be analyzed using Fisher's Exact test.

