Postpartum Non-pharmacologic Pain Management – Randomized Controlled Trial

Investigators: [name] (PI), [name], [name], DO, [name]

NCT03903172

Postpartum Non-pharmacologic Pain Management – Study Protocol

Investigators: [name] (PI), [name], [name], DO, [name]

Objective

To examine whether use of an abdominal binder for postpartum patients after vaginal delivery can effectively manage their pain and reduce the need for pharmacologic analgesics

Aims

1. To determine whether use of an abdominal binder on postpartum days zero and one will result in decreased patient pain as measured by pain scores on a visual analog scale of one to ten
2. To determine whether use of an abdominal binder for postpartum patients will reduce the quantity of non-narcotic pain medications given on postpartum day zero and one
3. To determine whether use of an abdominal binder for postpartum patients will reduce the quantity of narcotic pain medications given on postpartum day zero and one

Hypothesis

Use of an abdominal binder postpartum after a vaginal delivery will be associated with lower pain scores and reduced need for pharmacologic analgesics.

Background

A significant part of postpartum care involves management of patients' pain and discomfort. Etiologies of this pain include perineal pain, incisional pain, uterine involution pain, and pelvic girdle and lower back pain. Postpartum pain management primarily focuses on the former three types of pain: perineal, incisional and uterine involution. In a review of the management of postpartum pain, Eshkevari et al¹ discuss several well-established pain management strategies employed for postpartum patients, including ibuprofen and other NSAIDs for uterine involution pain and inflammation; local anesthetics for perineal lacerations or episiotomies; warm or cold compresses for perineal pain; and opioids for post-operative or poorly controlled postpartum pain.

Data regarding management of pelvic girdle and lower back pain is scarce and the limited literature available primarily focus on the pregnant patient. Different proposed treatment or management strategies

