the participant. The informed consent form will describe the project goals, length and rational, as well as the types of PHI that will be collected. All participants who agree to participate in the study will sign the informed consent form. All participants will be provided with a copy of the signed consent form.

- Study design & procedures
 - o After signing informed consent, participants will be assigned to the intervention or control group via block randomization
 - o Those participants in the standard of care group will receive routine postpartum care
 - o Those participants in the intervention group will receive an abdominal binder in addition to routine postpartum care
 - Determination of appropriate binder size will be based on a visual assessment of the patient's abdominal circumference
 - o Nursing staff will evaluate participant's pain level using a visual analog scale of 1-10 a minimum of every 4 hours. Patient reported pain score and pain location will be recorded in the participant's electronic medical record. These processes do not deviate from current standards of care and documentation.
 - o Additional non-pharmacologic pain relief measures utilized by patients will be documented on the data collection sheet attached to the patient's chart. These measures include heating pad, ice pack, and tucks pads
 - o All medications received will be documented in the electronic medical record per usual documentation protocols
 - o Nursing staff will document compliance of patient for wearing the abdominal binder, making notes when the binder was removed and if/when it was put back on.
- Sample Size Estimation & Data Analysis Plan
 - o Sample size was estimated using G*Power. In order to detect a difference between groups on pain scores and use of pain medications, we will need to enroll 65 patients per group. This will enable us to detect a moderate difference (i.e., medium effect size) between the groups with a power = 80% and p at <0.05. We will enroll an additional 10 patients to account for dropouts for a total N=140.
 - o The two groups will be compared for 1. reported pain scores (assessed by nursing staff and documented in the EMR) and for 2. pain medications used (morphine equivalent as

recorded in the MAR) for the duration of patients' hospital stay. Repeated measures analysis of variance will be used to determine differences between the groups over time.

- Data collection plan

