 - o Prospective data collection with hard copy data entry form that includes PHI for participant identification, basic demographic information, delivery information (see separate document), non-pharmacologic pain relief measures used
 - o Electronic medical record review for: pain scores, pain location, medications received
 - Pain score immediately postpartum
 - Pain scores on PPD#0 and PPD#1
 - Patient reported pain locations
 - Quantity of non-narcotic pain medication received on PPD#0 and PPD#1
 - Quantity of narcotic pain medication received on PPD#0 and PPD#1
 - Compliance wearing the abdominal binder
- Risks
 - o Allergic reaction to fabric of abdominal binder
 - o Skin irritation
 - o Increased discomfort or pain with use of abdominal binder
- Mitigation of risks
 - o If participants experience an allergic reaction or skin irritation from the abdominal binder they will be offered symptomatic treatment. Participants in the experimental arm will be encouraged to keep the abdominal binders in place for 24 hours postpartum, but will be permitted to remove the abdominal binder at any time should they find it causing irritation, increased pain or any other adverse reaction.

References

1. Eshkevari, L, et al. "Management of Postpartum Pain." *Journal of Midwifery and Women's Health*, vol. 58, no. 6, 2013, pp. 622–631.
2. Wu WH, et al. "Pregnancy related pelvic girdle pain (PGP), I: terminology, clinical presentation, and prevalence." *European Spine Journal*, vol. 13, 2004, pp. 575–589.

3. Vermani, E, et al. "Pelvic girdle pain and low back pain in pregnancy: a review." *Pain Practice*, vol. 10, no. 1, 2009, pp. 60-71.
4. Mens JMA, et al. "The mechanical effect of a pelvic belt in patients with pregnancy-related pelvic pain." *Clinical Biomechanics*, vol. 21, 2006, pp. 122-127.
6. Gillier, CM, et al. "A randomized controlled trial of abdominal binders for the management of postoperative pain and distress after cesarean delivery." *International Journal of Gynecology and Obstetrics*, vol. 133, 2016, pp. 188-191.
7. Ghana, S, et al. "Randomized controlled trial of abdominal binders for postoperative pain, distress, and blood loss after cesarean delivery." *International Journal of Gynecology and Obstetrics*, vol. 137, 2017, pp 271-276.

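### Does leaving postpartum days 0 and 1 undefined undermine the day 1 pain comparison, given that binder wear is encouraged for only 24 hours?

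*SAP*

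**What the plan says.** The SAP's second comparison is "study outcomes for average pain score on postpartum day 0 and postpartum day 1", and its second analysis item reads "Average pain scores on PPD0 and PPD1 will be analyzed using" a Student's t-test. The natural reading is one average per woman per day and one test per day. Neither the SAP nor the protocol's Data collection plan, which uses the same day labels, gives a start or end for either day.

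Three parts of the protocol bear on exposure:

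- Aim 1 asks whether "use of an abdominal binder on postpartum days zero and one will result in decreased patient pain".
- Mitigation of risks has the binder group "encouraged to keep the abdominal binders in place for 24 hours postpartum". It adds that any woman whom the binder troubles "will be permitted to remove the abdominal binder at any time". It sets no maximum.
- Study design & procedures has nurses record compliance, "making notes when the binder was removed and if/when it was put back on", and score pain on a "visual analog scale of 1-10 a minimum of every 4 hours".

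The sample size section plans 65 women per group, plus 10 in total for dropout, to "detect a moderate difference (i.e., medium effect size) between the groups" with 80% power.

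**The concern.** A daily average means little until the day is defined, and here the definition decides how much of day 1 overlaps the encouraged wear. If day 1 means hours 24 to 48 after delivery, none of it does. If it means the next calendar day, the overlap runs from almost nothing to almost all of the day, depending on the hour of birth.

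If binders come off at about 24 hours and relief stops with them, the day 1 test compares two groups of women who are largely not wearing a binder. Power falls, and a null result could mean either that the binder does not work or that it was not on.

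Calendar days raise a second worry. Day 0 then lasts anywhere from minutes to 24 hours, so some women's day 0 average could rest on very few scores.

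**Working it through.** **The plan's own figure.** Inputs from the sample size section: medium effect, 80% power, 5% level. I take d = 0.5 and a two-sided test, since neither is stated.

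- Normal approximation: n = 2(1.960 + 0.842)² / 0.5² = 62.8, so 63 per group.
- Exact t-test: 63.8, so 64 per group. The stated 65 is consistent with this, and 65 + 65 + 10 = 140.
- At 65 per group the noncentrality is 0.5 × √(65/2) = 2.85 on 128 degrees of freedom, giving 80.8% power.

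**Share of day 1 inside the wear period.** Let U be the hours from birth to midnight, taken as uniform on 0 to 24 (assumption), and r the hour of removal (assumption).

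- Calendar days: share = (r − U)/24, limited to 0 to 1. At r = 24 its mean is 0.50.
- 24-hour blocks: share = (r − 24)/24, limited to 0 to 1. At r = 24 it is 0.

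**Day 1 power.** Effect = 0.5 × mean share, 65 per group, no carry-over:

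| Removal (h) | Calendar: share, power | Blocks: share, power |
|---|---|---|
| 18 | 0.28, 13% | 0, 5% |
| 24 | 0.50, 29% | 0, 5% |
| 30 | 0.72, 53% | 0.25, 11% |
| 36 | 0.88, 70% | 0.50, 29% |
| 48 | 1.00, 81% | 1.00, 81% |

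Simulation with the share varying between women (calendar days, removal at 24 hours) gave 29% to 30%, so using the mean share does not distort the result.

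**Carry-over, removal at 24 hours.** If half the effect persists, the calendar-day effect is 0.5 × (0.5 + 0.5 × 0.5) = 0.375 (power 56%) and the block effect is 0.5 × 0.5 = 0.25 (power 29%). With full carry-over, power is 81% under either definition.

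**Discharge.** The table assumes a full 24-hour day 1, but pain is scored only in hospital. If women leave at 36 or 30 hours (assumptions), the mean calendar-day share at r = 24 rises to 0.53 or 0.62, and power to 32% or 42%. With blocks and discharge at 36 hours, day 1 is hours 24 to 36. Removal at 30 hours then covers half of it (29%, not 11%), and removal at 36 hours covers all of it (81%, not 29%).

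**Day 0.** It lies within the first 24 hours under either definition, so the wear mismatch does not touch it. Scores guaranteed by the 4-hourly minimum number floor(U/4) under calendar days: 0 to 5, each with probability 1/6. The mean is 2.5, with none for 1/6 = 17% of women and at most one for 2/6 = 33%. Blocks guarantee 24/4 = 6. These are floors: they leave out the immediate postpartum score and any extra assessments.

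**Would a tighter definition help?** Equal 24-hour windows from delivery are the block definition. For removal at 24 hours and no carry-over, that takes day 1 power from 29% to 5%, and it leaves the later window more exposed to discharge. The gain is an even count of day 0 scores.

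**The case for a change.** The strongest case for acting is that fixing the outcome window is what a SAP is for, and this one leaves it open. Aim 1 speaks of wear on both days while the only stated wear period is 24 hours. The arithmetic is sound and conditional in its wording. The compliance notes that could help explain a null day 1 result appear nowhere in the SAP, and the thin day 0 averages need no assumption about wear or carry-over.

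Much of this stands as description. The day is undefined, Aim 1 and the wear advice are in tension, and the figures follow from their inputs.

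The inference to a defective plan does not stand, for four reasons:

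- The protocol's medium effect is a difference between the groups, in a design that lets women remove the binder. Treating it as an effect only while worn, and then diluting it, replaces the planning assumption with another. On the protocol's own wording there is no loss.
- Twenty-four hours is encouragement without an upper limit, and re-application is recorded. A woman can follow that advice and still wear the binder on day 1, so no contradiction is proven.
- Under calendar days, 24 hours of wear from delivery reaches into both days for essentially every woman. Aim 1 fits that reading better, so the block figures belong to the less likely case.
- Uneven day 0 length affects precision and missingness, not bias, because hour of birth is balanced by randomization.

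**Conclusion.** No change to the plan is needed. The missing day definition is a detail an analyst can fill sensibly. Followed as written, the plan gives two valid comparisons by assignment, one for each day. The wear mismatch cannot bias either of them and does not reach day 0.

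The feared cost is lower power on day 1. Across the assumptions tried it runs from 5% to 81%, and the documents do not fix where in that range the trial sits. The low end needs an effect of d = 0.5 only while worn, removal at or before 24 hours, no carry-over and 24-hour blocks. Full carry-over, wear through day 1, or the protocol's between-group effect taken as stated each give the planned 81%.

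Fixed windows from delivery trade an even number of day 0 scores for a day 1 window wholly outside the encouraged wear, so they are not a clear improvement. The wording of Aim 1 and of Mitigation of risks must be reconciled by the sponsor, who decides the wear period. The two daily tests are valid whichever way that is settled. The recorded removal times are available to anyone who needs to interpret a null day 1 result.

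### Optional improvement: SAP item 2 could adjust pain for a pre-binder score already collected; the planned t-test is valid but leaves precision unused

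*SAP*

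**What the plan says.** The SAP's comparison list names "baseline characteristics including age and baseline pain score" and then "study outcomes for average pain score on postpartum day 0 and postpartum day 1". Analysis item 1 reads "Baseline age and postpartum pain scores will be analyzed using Student's T-test"; item 2 reads "Average pain scores on PPD0 and PPD1 will be analyzed using Student's T-test". No model with a covariate appears in the SAP. The protocol's Sample Size Estimation & Data Analysis Plan names a repeated measures analysis of variance, also without a baseline covariate.

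The protocol's Data collection plan lists "Pain score immediately postpartum" and, as a separate entry, "Pain scores on PPD#0 and PPD#1". Nurses score pain "using a visual analog scale of 1-10 a minimum of every 4 hours". On size, the protocol says "we will need to enroll 65 patients per group" for a medium effect, 80% power and p<0.05. Ten more women for dropout bring the total to 140.

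Neither document says which score is the SAP's baseline, when the binder is first applied, what the matching time is in controls, whether the immediate score also counts towards the PPD0 average, or how complete that score will be. The compliance notes described under Study design & procedures cover removal and re-application of the binder, not its first application. Women are approached before delivery and assigned once they have consented, and no blinding is described.

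**The concern.** A measurement of the outcome taken before treatment usually explains part of its variance. Putting it in the model narrows the confidence interval without another patient. Here such a score appears to be collected already, yet it is used only to test whether the groups differ at the start. That test does nothing for the precision of the treatment comparison.

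Two definitions decide whether the score can be used. If it is recorded after the binder goes on, adjusting for it removes part of the effect being estimated. If it precedes the binder but is averaged into PPD0, it dilutes the PPD0 difference under any test, because the binder cannot have changed it.

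**Working it through.** **Inputs.** From the protocol: 65 per group, medium effect, 80% power, p<0.05. Assumed: medium means d = 0.5 SD; the test is two-sided; r, the correlation between the baseline score and the daily average, runs from 0.2 to 0.7. The documents give no r.

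**1. The plan's own figure.** By the normal approximation, n = 2(1.960 + 0.842)²/0.5² = 62.8, so 63 per group; the noncentral t gives 63.8, so 64. The plan's 65 agrees. One-sided would need only 50, so the two-sided reading fits. Power at 65: noncentrality 0.5/√(2/65) = 2.850 on 128 df, giving 80.8%.

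**2. Adjusted analysis, complete scores.** The standard error is √[(1 − r²)(2/n)(1 + 1/(2n − 4))] in SD units. The last factor, 1 + 1/126 at n = 65, is the cost of estimating the slope. Noncentrality is 0.5 divided by this, on 127 df.

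| r | Noncentrality | Power | √(1 − r²) | CI narrower by about |
|---|---|---|---|---|
| 0.2 | 2.898 | 82.0% | 0.980 | 2% |
| 0.3 | 2.976 | 84.0% | 0.954 | 5% |
| 0.5 | 3.278 | 90.2% | 0.866 | 13% |
| 0.7 | 3.976 | 97.6% | 0.714 | 29% |

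The last column leaves out the slope cost, which widens the interval by about 0.4%. At r = 0 the adjusted power is 80.4%, a loss of 0.4 points.

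**3. Missing scores.** Compare the adjusted analysis in women who have a score with the unadjusted test in all 65 per group. At r = 0.2, with 2 missing in each arm (63 left), adjusted power is 80.8%, level with the t-test. With 3 missing in each arm it is 80.2%, below it. The break-even is therefore 2 per arm at r = 0.2. It rises to 5 at r = 0.3 and 15 at r = 0.5. As a rough check, the gain is lost once the missing share nears r²: 0.04 × 65 = 2.6, 0.09 × 65 = 5.9, 0.25 × 65 = 16.3.

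**4. Overlap with PPD0.** Suppose the PPD0 average held 6 equally weighted scores (one every 4 hours for 24 hours, an assumption) and one of them preceded the binder. A 0.50 SD difference would become 0.50 × 5/6 = 0.42 SD on the same scale, a loss of one sixth.

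**5. A score taken after the binder.** Suppose the binder had already lowered the covariate by 0.25 SD (assumed). The adjusted difference becomes 0.5 − 0.25r: 0.45, 0.425, 0.375 and 0.325 SD at r = 0.2, 0.3, 0.5 and 0.7. Dividing by the standard error in step 2 gives power of 73.5%, 70.9%, 68.4% and 72.7%. All are below the unadjusted 80.8%.

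**The case against.** The best case for leaving item 2 alone is that the t-test is already sound. Randomisation protects it and the sample size supports it. At r of 0.3 or less, adjustment buys only 1.2 to 3.2 points of power (82.0 − 80.8 and 84.0 − 80.8). The proposed covariate probably follows randomisation in a trial with no blinding described. The documents do not show that it precedes the binder, and the encouragement under Mitigation of risks to wear the binder for the first 24 hours fits early application. Step 5 shows that a wrong assumption about timing can cost more than low-r adjustment gains. Even a pre-binder score is patient-reported: if knowing the allocation shifted it by 0.1 SD (assumed), the adjusted estimate would move by 0.1r, or 0.02 to 0.07 SD over the same range of r.

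All of this stands. It is why the point is optional, why the covariate must be restricted to scores charted before the binder, and why the unadjusted result must always be shown. It does not remove the possible gain at moderate correlation, nor the need to define baseline, which item 1 requires as written.

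A reader might infer three stronger things that the documents do not support:
- **That the t-test is wrong or the trial is too small.** Step 1 shows otherwise.
- **That the PPD0 average contains the baseline score.** The Data collection plan lists the two separately, so this calls for clarification and is not a shown error.
- **That adjustment would certainly raise power much.** That depends on a correlation and on a completeness that the documents do not state.

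**Conclusion.** The point holds as an optional, low-cost improvement. With complete pre-binder scores at 65 per group, power would rise from 80.8% to between 82.0% and 97.6% as r goes from 0.2 to 0.7, with an interval about 2% to 29% narrower. This rests on d = 0.5, a two-sided test, the assumed r, and a score that the binder has not influenced. The gain is modest at r of 0.3 or less, and at r = 0.2 it is gone once more than 2 scores per arm are missing. If the score cannot be shown to precede the binder, the present t-test is the safer primary analysis.

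**What to change.** In SAP item 2, prespecify analysis of covariance on each day's average, or one mixed model for both days, with the immediate postpartum score as covariate. Align the protocol's repeated measures sentence with whichever is chosen. In the same text:

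- Define baseline as the immediate postpartum score charted before the binder is first applied, with a matching time in controls.
- State that this score is left out of the PPD0 average in both the adjusted and unadjusted analyses.
- Report the adjusted difference with a 95% confidence interval, and always show the unadjusted difference in all women beside it.
- Report missing pre-binder scores by group.
- Before outcomes are compared by group, check timing and completeness. If the scores cannot be shown to be pre-binder, or more than about 2 per arm are missing, the unadjusted t-test stays primary.
- In item 1, report baseline age and pain descriptively.

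The cost is wording in the SAP and protocol and no more patients. If charted times do not show which score came first, one time field on the data form would be needed. If data are already collected, only existing chart times can be used, and the plan may fall back to the present t-test.

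### The protocol tests pain by repeated-measures ANOVA and the SAP by Student's t-tests on PPD0 and PPD1 averages; neither says which governs or names a primary pain contrast

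*SAP*

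**What the plan says.** The protocol (Sample Size Estimation & Data Analysis Plan) compares the groups on reported pain scores and on medication use, and closes with "Repeated measures analysis of variance will be used to determine differences between the groups over time". It does not say how readings on a "visual analog scale of 1-10 a minimum of every 4 hours" become time levels, or whether the group effect or the group-by-time term is the test.

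The SAP (analysis item 2) has no repeated-measures model: "Average pain scores on PPD0 and PPD1 will be analyzed using" Student's t-test. It neither mentions the ANOVA nor says that it replaces it, and the protocol does not defer to a SAP.

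No contrast is ranked. Aim 1 asks whether "use of an abdominal binder on postpartum days zero and one will result in decreased patient pain", which covers both days. The sample size is set "to detect a difference between groups on pain scores and use of pain medications", with no day or summary measure singled out. The SAP lists the two days side by side.

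On baseline, the SAP compares the arms on "baseline characteristics including age and baseline pain score" but uses that score in no outcome analysis. The protocol's Data collection plan lists "Pain score immediately postpartum" separately from the PPD0 and PPD1 scores, so this is the natural candidate for the baseline.

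**The concern.** Pain is the first-listed aim, and the two documents give different tests for it. An analyst following them could report a PPD0 t-test, a PPD1 t-test, a test of the two-day average, an ANOVA group effect or a group-by-time interaction, and call any of them planned. These answer different questions and have different power. A reader of the results could not tell a prespecified pain finding from one picked among several candidates. If significance on either day were taken as success, the false-positive rate for pain would exceed 5%.

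**Working it through.** **Inputs from the protocol:** 65 per group, 80% power, p < 0.05, a medium effect with no number attached.

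**Assumptions, because the documents give no values:** two-sided testing; d = 0.5 for a t-test (Cohen's f = 0.25 for an ANOVA); between-day correlation rho; ratio k of the PPD1 effect to the PPD0 effect. All illustrations use two complete daily averages per patient.

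**1. Reproduce the plan's figure.** A two-sample t-test at d = 0.5, two-sided 0.05 and 80% power needs 63.8, so 64 per group. At 65 per group the noncentrality is 0.5 × sqrt(65/2) = 2.85 on 128 df, and power is 80.8%. The between-group test of a repeated-measures ANOVA at f = 0.25, with noncentrality N f² m / (1 + (m − 1) rho), needs a total N of only 48 to 110 for m = 2 to 12 levels and rho = 0.3 to 0.7. The planned 130 before dropout therefore fits one t-test contrast and does not fit that ANOVA test.

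**2. Compare the candidate tests** (noncentral t, 128 df):
- PPD0 alone: d = 0.5.
- PPD1 alone: d = 0.5k.
- Two-day average: d = 0.5 × (1 + k)/2 ÷ sqrt((1 + rho)/2). With two complete daily averages this is the same test as the ANOVA group effect.
- Group-by-time: d = 0.5 × (1 − k) ÷ sqrt(2(1 − rho)).

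At rho = 0.5 the divisors are sqrt(0.75) = 0.866 and sqrt(1) = 1:

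| Test | Equal effect (k = 1) | Half effect on PPD1 (k = 0.5) |
|---|---|---|
| PPD0 | d 0.50, 81% | d 0.50, 81% |
| PPD1 | d 0.50, 81% | d 0.25, 29% |
| Two-day average | d 0.577, 90% | d 0.433, 69% |
| Group-by-time | d 0, 5% | d 0.25, 29% |

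The two-day average beats PPD0 only if k exceeds 2 × sqrt((1 + rho)/2) − 1, which is 0.73 at rho = 0.5. No candidate is best in both columns.

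**3. How often the verdicts differ.** In 40,000 simulated bivariate-normal trials per scenario, the PPD0 test and the two-day average disagreed on significance in about 15%, 12% and 9% of trials at rho = 0.3, 0.5 and 0.7 with an equal effect. With a half effect on PPD1 the figures were about 16% to 18%.

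**4. False positives if either day counts.** Two tests at 0.05 give 1 − P(|Z1| < 1.96 and |Z2| < 1.96). At rho = 0 this is 1 − 0.95² = 9.75%. At rho = 0.3, 0.5, 0.7 and 0.9 it is 9.5%, 9.1%, 8.3% and 7.0%.

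**5. Secondary: adjusting one day's score for baseline.** d = 0.5 ÷ sqrt(1 − r²) on 127 df, where r is the baseline-to-outcome correlation. At r = 0.2, 0.3 and 0.5, d is 0.510, 0.524 and 0.577, and power rises from 81% to 82%, 84% and 90%.

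**The case against.** **The documents also differ on the time window.** A reader might infer this from "recorded in the MAR) for the duration of patients' hospital stay". The text does not establish it. That phrase follows the medication item and may apply only to it, while Aim 1 and the Data collection plan already confine pain to PPD0 and PPD1. The clear conflict is one of method.

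**The SAP is dated and might be presumed to govern.** That is reasonable, but neither document says so. Even if it does govern, it leaves two unranked days. Two tests is its natural reading, although one combined average is possible.

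**The two methods can coincide.** They do so only for the ANOVA group effect with two complete daily averages, set against a t-test on each patient's two-day average. The protocol specifies neither daily averages nor two levels.

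**The figures rest on assumptions, and any two non-identical tests sometimes disagree.** Both statements are true. The numbers show that the choice matters, not that either test is faulty. If the PPD1 effect were nil, disagreement would reach 40% to 47%, but that is an extreme bound. PPD0 is not defined, and the 24 hours of encouraged wear (Mitigation of risks) may run into PPD1.

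**Baseline adjustment is a preference.** It is partly that. The gain is negligible at r of 0.2 or below, and the documents do not show that the score precedes binder fitting. It stays as a secondary, conditional point, because the SAP itself calls the score baseline and then makes no further use of it.

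**Conclusion.** The concern holds as a conflict of method together with an unnamed primary contrast. It should be resolved, although each test is valid taken alone. In the two scenarios tabulated, over assumed correlations of 0.3 to 0.7, the choice between the PPD0 test and the two-day average changes the significance verdict in about 9% to 18% of trials.

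The 7% to 10% false-positive figure depends on an either-day success rule that neither document states, so it measures what the silence permits and is not an established error rate of the plan. Two stronger conclusions are also unsupported. The sample size is not shown to be wrong, since 65 per group gives 81% power for one t-test if medium means d = 0.5. Leaving baseline out does not bias the comparison; it only forgoes precision. Confidence in the textual conflict is high. The size of its effect rests wholly on the assumed effects and correlations.

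**What to change.** - State one governing pain analysis in both documents, and say whether the SAP's t-tests replace the protocol's ANOVA.
- Before arm-level data are examined, name one primary contrast: PPD0, PPD1 or the two-day average. Report it as a mean difference with a 95% CI and label the other contrasts secondary. If arm-level data have already been seen, label the choice post hoc.
- If the ANOVA is kept, define its time levels and say which term is tested.
- Secondary: if the immediate-postpartum score was recorded before the binder was fitted, adjust the pain comparison for it by ANCOVA and keep it out of the PPD0 average. If that order cannot be confirmed, keep the unadjusted comparison and say so.

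Cost: wording in both documents, one model term, and possibly a chart check. Study design & procedures has nurses note removal and replacement of the binder but does not mention first fitting. N does not change.
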